1.0 Research Design

1.1 Purpose/Specific Aims

The overall purpose of the study is to test the effect of metformin on exercise intensity based training adaptations in adults with metabolic syndrome.

A. Objectives

Understand effect of metformin on training intensity mediated vascular versus metabolic insulin sensitivity in adults with metabolic syndrome for clinical health.

B. Hypotheses / Research Question(s)

The overarching hypothesis is that metformin may blunt adaptation following high intensity exercise by lowering/attenuating oxidative stress. Thus, compared with high intensity exercise plus metformin, low intensity exercise plus metformin will produce greater vascular insulin sensitivity and metabolic insulin sensitivity changes following 16 weeks of treatment. In addition, we anticipate that high intensity exercise based training alone will produce greater effects than low intensity exercise. Lastly, we hypothesize that these changes in metabolic and vascular insulin sensitivity will correlate with glycemic control and blood pressure changes.

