 - Subjects will be required to wear clothes without metal on them (including zippers and bras with an underwire). If clothes have metal, we will ask that subjects change into a pair of shorts and a t-shirt or wear a lab hospital gown.
 - If there are technical issues with the DEXA machine we will measure the total amount of fat and muscle in the subjects body with the BodPod® in the IFNH.
 - We will provide a swimsuit and swim cap for subjects to wear during this procedure to help standardize the results. The swimsuit and swim cap are provided to get accurate results. Subjects will not get wet at any time during this test. Subjects will enter the device and sit down. A door will close while the subject sits in the BodPod®. They are asked to breath normal and be still. The BodPod® looks like a large white egg with a window on the door.

NOTE: in the event of scheduling conflicts, cardiovascular fitness and/or body composition assessments may be completed within 1 week of doing the OGTT during Visit 58.

END OF STUDY:

After subjects have completed Phase 5, the study will be complete.

B. Data Points

We are collecting blood and urine during experimental visits. Vital signs, including blood pressure, temperature, heart rate, as well as aerobic fitness, body composition, resting metabolism, non-exercise physical activity, appetite, as well as quality of life. Please see the study overview (Study Duration) that outlines when outcomes will be collected.

C. Study Duration

Subjects participation in this study will require about **58** study visits over about 7-8 months. Each visit will last between **1-6** hours depending on whether it is for research purposes (e.g. about 3-6 hours) or exercise training (e.g. 1-1.5 hours). There are 2 Screening Visits and 5 Test Visits. Thus, the majority of visits include exercise training (48 visits).

D. Endpoints

The primary outcome for this study will be changes of basal FMD before the insulin clamp pre and post intervention. We will also examine the influence of insulin on FMD as well as metabolic insulin sensitivity, defined as the glucose infusion during the last approximate 30 minutes of the clamp procedure. Together, these findings will help tease out vasculature vs. metabolic insulin sensitivity differences between treatments. Correlations will be conducted to understand the relationship between endothelial function and metabolic insulin sensitivity with substrate oxidation,

12/31/2499

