1.4 Preliminary Data

We do have not have preliminary data on endothelial function with metformin combined with exercise. However, our preliminary work in Met/prediabetic individuals shows that when metformin is combined with HiEx there tends to be a blunting effect on skeletal muscle metabolic insulin resistance ^{4,5,33}. Furthermore, we previously showed that metformin blunted HiEx-induced improvements in blood pressure and hs-CRP vs. HiEx only. Together, along with literature from other investigators, it reasons endothelial function may be impacted by metformin plus exercise.

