1.6 Study Variables

A. Independent Variables, Interventions, or Predictor Variables

This is a randomized by sex, double-blind, placebo controlled trial. A placebo is needed to minimize potential behavioral changes with pharmacological intervention. This will isolate the effects of exercise intensity based training on respective outcomes. As a result, exercise at low or high intensity with placebo will serve as standard of care/control, while exercise at low or high intensity with metformin will be the experimental conditions. Pre and post test data will be compared statistically.

Data will be analyzed using R (Vienna, Austria, 2011). A two-way repeated measures analysis of variance (ANOVA) will be used to assess time course differences (group x test). Bonferonni post-hoc analysis will be used to determine group differences and paired t-tests will be used to assess within treatment effects. Linear regression analyses will be used to identify relationships between respective variables. A *P*<0.05 will be considered statistically significant. Data will be expressed as mean ± SEM.

12/31/2499

The same statistical approach for secondary analysis will be conducted as the primary variable analysis.

B. Dependent Variables or Outcome Measures

- 1. Insulin Sensitivity
- 2. Fitness (e.g. VO2max, physical activity amount, heart rate, RPE, etc.)
- 3. Body composition (e.g. weight, fat, FFM, BMD, waist circumference, etc.)
- 4. Vascular Function (e.g. FMD, CEU, heart, arterial stiffness, etc.)
- 5. Questionnaires (e.g. Sleep, activity, quality of life, hunger, etc.)
- 6. Glucose (e.g. substrate, isotope)
- 7. Lipid Profile (e.g. TG. HDL. FFA. etc.)
- 8. Blood clinical chemistries (e.g. CBC)
- 9. C-peptide
- 10. Insulin
- 11. Inflammation (e.g. endothelin-1, adiponectin, Microparticles, etc.)
- 12. Nitrates
- 13. Gut hormones (e.g. ghrelin, GLP-1, etc.)
- 14. Pregnancy (in females), blood for screening at each admission.
- 15. Energy metabolism (e.g. rest, exercise, insulin-stimulation).
- 16. Gut microbiota
- 17. Cognitive measures using NIH toolbox

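### The change-on-change regressions do not say how treatment arm is handled; if the arms are pooled, treatment effects alone can create or hide an association

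*Combined protocol and SAP*

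**What the plan says.** The last hypothesis in section 1.1 B is that "these changes in metabolic and vascular insulin sensitivity will correlate with glycemic control and blood pressure changes". Section 1.3 D widens this: "Correlations will be conducted to understand the relationship between endothelial function and metabolic insulin sensitivity with substrate oxidation", and the list continues with inflammation, blood pressure, glycaemic control, body composition, fitness and quality of life.

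Section 1.6 A gives the whole method in one sentence, "Linear regression analyses will be used to identify relationships between respective variables", with the general criterion "A *P*<0.05 will be considered statistically significant". It names no arm factor, no within-arm analysis and no covariate. The sentence on secondary outcomes, "The same statistical approach for secondary analysis will be conducted as the primary variable analysis", adds nothing about arm in the regressions. Section 6.1 (Data Analysis) contains only the template prompt.

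The protocol also expects the arms to differ on both sides of these regressions. For insulin sensitivity, section 1.1 predicts that "compared with high intensity exercise plus metformin, low intensity exercise plus metformin will produce greater vascular insulin sensitivity and metabolic insulin sensitivity changes". For blood pressure, section 1.4 reports that "metformin blunted HiEx-induced improvements in blood pressure and hs-CRP vs. HiEx only", and section 1.5 cites a significant blunting of systolic pressure with 8 people per group.

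**The concern.** When treatment moves two outcomes, the arm means of the two changes line up. A regression across all subjects that ignores arm then picks up a slope from those means, even if inside each arm a subject's change on one outcome says nothing about the change on the other. If the arm effects run against a true within-arm link, the pooled slope can cancel it.

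This trial fits the condition. The contrast between high-intensity exercise with and without metformin is expected to move insulin sensitivity and blood pressure together. A significant pooled slope could then be read as evidence that the two changes are linked within people, when it only shows the treatment effect on each. What is at stake is the last stated hypothesis and the correlational findings of section 1.3 D.

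**Working it through.** **Inputs.** From section 1.5: 15 evaluable subjects per arm, SD of FMD change 3.4%, detectable difference 4.2%, 80% power, Bonferroni over 6 pairs. From section 1.3: four arms, equal allocation. From section 1.6: P<0.05 (two-sided assumed). The documents give no standardised arm effect for clamp insulin sensitivity, glycaemia or blood pressure, so those shifts are assumed and varied.

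**Step 1. The plan's own figure.** Two-sided normal approximation with alpha 0.05/6 = 0.00833: (2.638 + 0.842) × 3.4 × √(2/15) = 4.32%, against the stated 4.2%. The sample size for 4.2% is 2 × (3.480 × 3.4/4.2)² = 15.9, so 16 per arm against the stated 15. That is close enough to use 4.2/3.4 = 1.24 SD as a yardstick. It is a minimum detectable difference for basal FMD, not an expected effect, and it belongs to no other outcome.

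**Step 2. Closed form.** Take zero within-arm correlation and the same arm shifts, in SD units, on both variables. The large-sample pooled correlation is r = V/(V + 1), where V is the variance of the four arm means. The pooled rejection rate is roughly Φ(atanh(r) × √(60 − 3) − 1.96). At a shift of 1.24 SD (1.235² = 1.526):

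| Arm pattern | V | Pooled r | Approximate rejection |
|---|---|---|---|
| Two arms against two | 1.526/4 = 0.38 | 0.28 | 57% |
| One arm different | 1.526 × 3/16 = 0.29 | 0.22 | 40% |
| Four equally spaced | 1.526 × 0.139 = 0.21 | 0.17 | 27% |
| Two extremes, two midway | 1.526/8 = 0.19 | 0.16 | 23% |

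**Step 3. Simulation.** 20,000 trials per setting, 15 per arm, unit-variance normal changes, zero within-arm correlation, pooled test on 58 df. The first variable differs by 1.24 SD; the second follows the same arm pattern with the shift shown. Entries are rejection rates.

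| Arm pattern | 0 | 0.31 SD | 0.62 SD | 0.93 SD | 1.24 SD |
|---|---|---|---|---|---|
| Two against two | 5.1% | 9.5% | 22.5% | 41.0% | 59.7% |
| One arm different | 4.8% | 7.8% | 15.2% | 27.0% | 41.3% |
| Four equally spaced | 5.1% | 6.7% | 11.2% | 18.5% | 27.1% |
| Two extremes, two midway | 4.7% | 6.4% | 10.0% | 15.9% | 23.2% |

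The last column agrees with Step 2. Other settings:
- Both variables shifted by only 0.62 SD: 10.1%, 7.8%, 6.6% and 6.3%, in the same row order.
- Both shifted by 1.24 SD but on unrelated arm contrasts: 4.4%, so no inflation.
- Shifts of opposite sign: the same rates with a negative r.

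**Step 4. Arm in the model.** With the four-level factor (60 − 5 = 55 df), the rejection rate is 4.7% to 5.3% in every zero-correlation setting.

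**Step 5. Masking.** With a true within-arm correlation of 0.4 and opposing two-against-two shifts of 1.24 SD, the pooled test is significant in 3.4% of trials and the arm-adjusted test in 88.5%.

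**The case against.** The strongest reply is that the plan never says the arms are pooled. A regression with an arm factor, or one per arm, also fits the sentence in section 1.6. That stands: a reader might infer that the protocol commits to an unadjusted model, and the text does not support it. What remains is that the plan's only wording describes a relation between two variables, nothing elsewhere adds arm, and the choice stays open until the data are seen.

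Second, a pooled correlation is a real marginal association. It answers whether treatments that improve one outcome more also improve the other more, and neither section 1.1 nor section 1.3 D says that a within-arm link is meant. This also stands. The pooled result misleads only when it is read as a subject-level link.

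Third, the 60% figure needs 1.24 SD on both variables, the most favourable of the arm patterns tried, and exactly zero within-arm correlation. A reader might take it as the expected error rate. The documents do not support that, because 4.2/3.4 concerns basal FMD alone and the preliminary blood pressure results give direction, not size.

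A reader might also infer that success on the primary endpoint makes a spurious correlation likely. It does not by itself: with FMD shifted by 1.24 SD and the second variable unmoved, the rate is about 5%.

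**Conclusion.** The point holds as an under-specified secondary analysis whose natural reading is open to a known artefact. It does not show that the trial will report a false correlation. If the arms are pooled and no within-arm link exists, the chance of a significant slope with 15 per arm runs from about 5% to about 60%. Where it falls depends on whether both outcomes respond, how strongly, and whether their arm patterns align. The protocol predicts responses on both sides in direction but gives no sizes, so no single figure in that range can be called the expected one. The opposite error, a missed true link, arises when arm effects oppose it. An arm factor removes the inflation in every setting examined. The calculations assume normal changes with equal variance in all arms. The primary FMD comparison is not affected.

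**What to change.** Add to section 1.6 A that every change-on-change regression includes the four-level treatment arm as a factor, and that the common within-arm slope with its 95% CI is the test of a subject-level link. Any pooled correlation may be reported beside it, labelled as a marginal association that includes the treatment effect. In sections 1.1 B and 1.3 D, say which of the two questions the correlations are meant to answer.

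The cost is a few sentences and three degrees of freedom (58 to 55 with 60 subjects). It needs no new data, visits or subjects.

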1.7 Drugs/Devices/Biologics

A. Drug/Device Accountability and Storage Methods

All items will be kept in locked rooms in encrypted storage cabinets/refrigerators as appropriate. Access will only be allowed for research personnel. Overall, the PI has responsibility for storage and/or preparation as well as dispensing. Research personnel will assist with distribution/storage. Preparation will be performed by the PI, clinical coordinator and/or Clinical Research Pharmacist accordingly.

Metformin/placebo will be picked up at the Clinical Research Center. Items may be stored in Clinical Research Center and/or Loree for distribution to subject.

Insulin will be stored in the Clinical Research Center.

Definity microbubbles/Dextrose will be stored at Loree and/or Clinical Research Center.

1.8 Specimen Collection

A. Primary Specimen Collection

- Types of Specimens: Blood will be collected by trained research personnel in the study. Plasma or serum will then be stored for later use/analysis. Total volume collected will be approximately 125 cc for clamp protocol and 50 cc for OGTT protocol. Blood will be collected in the Clinical Research Center and/or IFNH as described below.
- Annotation: Each specimen will be coded with a unique identifier per the study, time point blood was collected (e.g. 0 min, 90 min, etc.) test (e.g. pre or post) and analyte. No personal identifier will be used.
- Transport: Specimens will be transported using biohazard containers properly marked on ice by Research Personnel on the IRB.
- Processing: Research Personnel.

Expiration Date:

12/31/1799

12/31/2499

- **Storage**: Specimens will be stored in the Clinical Research Center and/or IFNH accordingly. They will be accessed only by individuals with approved access by research personnel approved via the IRB.
- Disposition: Samples will be discarded when meeting study completion. Other samples kept will be placed in our freezer Research Repository.

B. Secondary Specimen Collection

NA

1.9 Data Collection

A. Primary Data Collection

- Location: questionnaire data will be collected in Loree, IFNH and/or Clinical Research Center as well as at home when appropriate. Permission will be granted by the subject.
- Process of Data Collection: Research personnel approved to work on this protocol to administer and collect data. The PI will oversee the process.
- Timing and Frequency: See below for details.
- Procedures for Audio/Visual Recording: NA.
- Study Instruments: Questionnaires are widely used and routine for this type of research.
- Ethnographic Studies, Interviews, Or Observation: Paper questionnaires will be used.
- Subject Identifiers: Each specimen will be coded with a unique identifier per the study, time point collected (e.g. 0 wk, 4 wk, etc.) and test (e.g. pre or post) will also be included. No personal identifier will be used on the forms.

B. Secondary Data Collection

NA

1.10 Timetable/Schedule of Events

Study Screening and Testing Schedule Visit Overview.

Study Visit	Screening Visit 1	Screening Visit 2	Pre- Test OGTT Visit 3 or 4	Pre- Test Clamp Visit 3 or 4	Exercise Training (Intervention Period) 5 d/wk* Visits 5-53	Post- Intervention Clamp Testing Visit 54	Post- Intervention OGTT Testing Visit 55-56	Follow up Week 4 check- in Visit 57	Follow up Week 8 OGTT Testing Visit 58
Informed Consent	X								
Blood Draw	X		X	Χ		X	X		х
History and Physical		X							
Urine Collection			X	X		X	X		X
VO2peak (Treadmill testing)		X					X		X
Body Fat measurement (Waist and Hip circumference,		X					Х		X

12/31/1799

12/31/2499

Approval Date:

DEXA or Bod Pod)								
Indirect Calorimetry	Х	·	X		X			X
Exercise* Indirect Calorimetry				X*	X			
24 hour Blood Pressure		Х		X*				
Blood Pressure, AI, CEU and PWV tests			X		X			X
FMD, CCA-IMT		Χ	Χ		X		-	Χ
Muscle/Fat Biopsy		·	Х		X			
Diet Record	X			Χ		X	Х	Χ
Appetite Questions		Х		X		X		Х
Quality of Life Questions		Х				X		Х
NIH Toolbox		Χ				Х		Χ
Accelerometer	X			Χ	_		Х	Х
Heart Rate Monitors				Χ			x	

Exercise Training will be performed at Loree Gymnasium or IFNH on Cook-Douglas Campus 3 days/week and supervised by an exercise physiologist/research team member. The other 2 days will be non-supervised as you will be asked to wear a heart rate monitor. Accelerometers will be provided for weeks 0, 8, 16, 20, 24. *Exercise Indirect calorimetry will include measures of breath samples the first day of training and within the last weeks of training.

2.2 Research Staff Training

Weekly meetings will be performed with the clinical coordinator and graduate students working with the PI to discuss protocols, data collection and subject adherence. Lab protocols will be implemented with direct oversight by the PI. Students and staff will receive appropriate training for such measurements and require sign off by the PI prior to direct data collection. Faculty with expertise in given areas will also be consultant in the lab protocol and will be communicated with at time of and throughout data collection as appropriate.

Faculty Co-I's will also meet regularly with the PI. For instance, monthly meetings will be held with all investigators during the first quarter of the study to establish/maintain continuity of the research. Thereafter, quarterly meetings with all investigators will be performed to maintain communications and updates on the study.

Individual faculty/staff/students will lastly receive a roles and responsibilities overview for the study, whereby agreements will be had to enhance communication and clarity on said duties.

Nurses and pharmacist of the Clinical Research Center will also be provided with copies of our protocols and the PI will review procedures to ensure communications.

2.3 Resources Available

Expiration Date:

12/31/1799

12/31/2499

NA

2.4 Research Sites

All research will be conducted at Rutgers (e.g. Loree, IFNH and/or CRC) as described.

3.0 Multi-Center Research

NA

4.0 Subject Considerations

4.1 Subject Selection and Enrollment Considerations

A. Method to Identify Potential Subjects

Prospective subjects will be recruited through posted and/or mailed flyers. Please see attached flyer that will be included in newspapers, Instagram, Reddit, Facebook or twitter as well as mailings via coldcontacts. Cold-contacts may be iniatited via use of electronic medical records using inclusion/exclusioncriteria through the Rutgers Robert Wood Johnson Medical School Endocrinology/Cardiology platforms (connected with [name] and [name]). Additionally, ResearchMatch.org will be utilized as a recruitment tool for this protocol. ResearchMatch.org is a national electronic, web-based recruitment tool that was created through the Clinical & Translational Science Awards Consortium in 2009 and is maintained at Vanderbilt University as an IRB-approved data repository (see IRB #090207). We will also use Trialfacts, a specialized patient recruitment service that combines extensive marketing and advertising expertise with in-depth clinical trial experience in order to aid research groups in successful study recruitment. Trialfacts uses digital advertising and specialized targeted ads based on eligibility criteria and online questionnaire data collection with specific software.

B. Recruitment Details

Prospective participants will be recruited using listservs and flyers across Rutgers University campus as well the Rutgers Robert Wood Johnson Medical School ([name].

We will also place flyers IRB approved in the New Brunswick and surrounding community at participating stores/libraries/etc. Newspapers (e.g. New Brunswick Today) and social media (Twitter, Facebook) will also be contacted about placing the flyer as an insert or respective info. Interested individuals will be asked to contact the research team by phone to get a more detailed description of the study. Prospective participants will be scheduled for a screening visit to establish eligibility. Enrollment will be decided after chemistry panel, blood pressure and waist circumference results are confirmed for group assignment. This will be evaluated by the PI, study physician and research team.

C. Subject Screening

Inclusion Criteria for Subjects

- Male or female >40 and <80 years old.
- Has a body mass index >25 and <47 kg/m².
- Not diagnosed with Type 2 diabetes.
- Not currently engaged in > 150 min/wk of exercise
- At minimum, subject will have abdominal obesity (increased waist circumference as defined below) and may have any additional National Cholesterol Education Adult Treatment Panel III Metabolic Syndrome criteria:
 - o Increased waist circumference (≥102 cm in men; ≥88 cm in women)

12/31/2499

- Elevated triglycerides (≥150 mg/dl), or on medication for treating the condition
- Reduced HDL-cholesterol (<40mg/dl in men, <50 mg/dl in women), or on medication for treating the condition
- o High blood pressure (≥130 mmHg systolic or ≥85mmHg diastolic), or on medication for treating the condition
- Elevated fasting glucose (≥100 mg/dl), or on medication for treating the condition
- Other major risk factors to be noted based on the Framingham Risk Score
 - HbA1c 5.7-6.4%
 - LDL > 130 mg/dL
 - Family history of type 2 diabetes (immediate family, i.e. parent/sibling)
 - History of gestational diabetes
 - History of Polycystic Ovarian Syndrome
 - Family history of pre-mature cardiovascular disease (immediate family i.e. parent/sibling) before 55 for males or 65 for females that can include heart attack, peripheral arterial disease, abdominal aortic aneurysm, symptomatic carotid artery disease or clinical coronary heart disease)
 - Age (> 45 years old for men; > 55 years old for women)
 - Black/African American, Mexican, Asian, and/or Hispanic
- Subjects currently taking medications that affect heart rate and rhythm (i.e. Ca++ channel blockers, nitrates, alpha- or beta-blockers)

Exclusion Criteria for Subjects

- Morbidly obese patients (BMI >47 kg/m²) and overweight/lean patients (BMI <25 kg/m²)
- Evidence of type 1 diabetes and diabetics requiring insulin therapy.
- Subjects who have not been weight stable (>2 kg weight change in past 3 months)
- Subjects who have been recently active (>30 min of moderate/high intensity exercise, 2 times/week).
- Subjects who are smokers or who have guit smoking <5 years ago
- Subjects prescribed metformin or have taken metformin within 1 year.
- Subjects with abnormal estimated glomerular filtration rate (eGFR).
- Hypertriglyceridemic (>400 mg/dl) and hypercholesterolemic (>260 mg/dl) subjects
- Hypertensive (>160/100 mmHg)
- Subjects with a history of significant metabolic, cardiac, congestive heart failure, cerebrovascular, hematological, pulmonary, gastrointestinal, liver, renal, or endocrine disease or cancer that in the investigator's opinion would interfere with or alter the outcome measures, or impact subject safety.
- Pregnant (as evidenced by positive pregnancy test) or nursing women
- Subjects with contraindications to participation in an exercise training program
- Currently taking active weight suppression medication (e.g. phentermine, or listat, lorcaserin, naltrexone-bupropion in combination, liraglutide, benzephetamine, diethylpropion, phendimetrazine)
- Known hypersensitivity to perflutren (contained in Definity)
- Subjects who are considered non-English speaking individuals

UPLOAD to e-IRB Section 11.0 Recruitment Materials - \underline{all} recruitment materials, such as: in-person or telephone scripts, emails, flyers, posters, social media posts, and radio or television advertisement scripts, etc. that will be used to recruit individuals to the study.

